**Table 6 Date of Progression or Censoring for DOR**

Situation	Date of progression or censoring	Outcome
Death or disease progression between planned disease assessments	Date of death or first disease assessment showing disease progression, whichever occurs first	Event
Surgical resection or subsequent anticancer treatment started before disease progression or death (without disease progression beforehand)	Date of last disease assessment prior to surgery or start of subsequent anticancer treatment	Censored
Death or disease progression after missing two or more consecutively scheduled disease assessments	Date of last disease assessment visit without documentation of disease progression before the first missed visit	Censored
Alive and without disease progression	Date of last disease assessment	Censored

- Mean change (%) in tumour volume at 6 weeks after each  $^{177}\text{Lu}$ -OPS201 administration (each cycle) compared to baseline, as assessed by volumetric CT/MRI.
- OS at 1-year and 2-year follow-up as determined from start of study treatment until occurrence of death of any cause. Subjects who were lost to follow-up or who were still alive at the time of analysis will be censored at the last day the subject was known to be alive or data cut-off date, whichever occurs first. OS will be calculated as follows:
  - OS (months) = (Death or Censoring Date – First Dose Date + 1)/30.4375
  - Quantitative changes (SUV normalised by lean body mass ( $\text{SUL}_{\text{max}}$  and  $\text{SUL}_{\text{mean}}$ ) in tumour-to-background  $^{18}\text{F}$ -FDG-PET uptake using PERCIST version 1.0, from Screening to 6 weeks after second  $^{177}\text{Lu}$ -OPS201 administration (second cycle).
  - Change in  $^{68}\text{Ga}$ -OPS202 uptake on PET scan after the second  $^{177}\text{Lu}$ -OPS201 administration (second cycle) as assessed by  $\text{SUV}_{\text{max}}$  and  $\text{SUV}_{\text{mean}}$  in subjects screened for  $^{177}\text{Lu}$ -OPS201 treatment as compared to clinical response and ORR.
  - Correlation between tumour uptake on  $^{68}\text{Ga}$ -OPS202 PET/CT (assessed based on  $\text{SUV}_{\text{max}}$  and  $\text{SUV}_{\text{mean}}$ ) at screening with tumour response to  $^{177}\text{Lu}$ -OPS201 therapy from Screening to 6 weeks after second  $^{177}\text{Lu}$ -OPS201 administration (second cycle).
  - Correlation between the uptake of  $^{68}\text{Ga}$ -OPS202 in tumour lesions expressing sstr2 on PET/CT images and the uptake on  $^{177}\text{Lu}$ -OPS201 SPECT/CT.
  - Proportion of subjects with sstr2-positive tumour lesions by  $^{68}\text{Ga}$ -OPS202 PET/CT scans as assessed by the identification of avid lesions in subjects screened for  $^{177}\text{Lu}$ -OPS201 treatment at baseline.
  - Diagnostic sensitivity of  $^{68}\text{Ga}$ -OPS202 imaging using RECIST by subject-based analysis.
  - Diagnostic sensitivity of  $^{68}\text{Ga}$ -OPS202 imaging by using mGa-RECIST by subject-based analysis.
  - Diagnostic sensitivity of  $^{68}\text{Ga}$ -OPS202 imaging by subject-based, organ-based and lesion-based analysis compared to standard-of-truth (SOT) of ceCT (or ceMRI).
  - Diagnostic sensitivity of  $^{68}\text{Ga}$ -OPS202 imaging by both organ-based and lesion-based analysis compared to standard-of-truth (SOT) of  $^{177}\text{Lu}$ -OPS201 SPECT/CT.

### Subject Reported Outcomes

Changes in health-related quality of life scores from baseline to EOCT measured by EQ-5D-5L and EORTC QLQ-C30.

#### **3.1.3 Safety endpoints**

Safety and tolerability measured by the type, nature, severity, expectedness and frequency of AEs overall and per grade according to the current version of the NC-CTCAE (version 5.0) and significant laboratory abnormalities.

Pharmacokinetics, biodistribution and dosimetry endpoints and measurement timepoints for phase II will be defined according to the phase I results.

#### **3.1.4 Exploratory endpoints**

##### **Phase I/II**

###### Biomarkers

- Association between the uptake on Ga-OPS202 PET/CT with sstr2 expression on tumours as determined by IHC.
- Change in renal safety biomarkers compared to baseline.
- Change from baseline in tumour microenvironment, transcriptomics, DNA repair, gene mutations and other disease markers of interest.
- Change from baseline in DNA repair capacity in blood.

###### Biobanking

The exploratory endpoint comprises biobanking of samples for future analysis, among subjects who consent. Analysis of additional biomarkers from the biobank samples will be performed outside the scope of the main study and reported separately.

Serum and whole blood ribonucleic acid (RNA) samples will be collected during screening, on Day 1 of Cycle 2 and at EOCT visit.

Instructions for collection, processing, handling and shipment of the banking samples will be outlined in the laboratory manual.

#### **3.1.5 Multiplicity**

No multiple testing will be performed in this study.

Therefore, type I error will not be adjusted.

#### **3.1.6 Significance testing and estimation**

As this is a descriptive safety and tolerability study, no formal statistical testing of safety will be carried out.

### **3.2 Analysis methods**

#### **3.2.1 Efficacy**

##### **3.2.1.1 Therapeutic Efficacy of Lu-OPS201**

Tumour response will be evaluated by the ICL. Phase I analyses on tumour responses will be using the MTCA evaluable population. Phase II analyses on tumour responses will be using the ITT population and the PP population.

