### **Treatment Period - Phase I**

Phase I is a multicentre, open-label, single-arm study designed to primarily investigate the safety and tolerability of  $^{177}\text{Lu}$ -OPS201 following fractionated i.v. administrations in pretreated subjects with locally advanced or metastatic cancers expressing sstr2 as identified by  $^{68}\text{Ga}$ -OPS202 PET/CT scans. This phase will encompass both radioactivity escalation and peptide mass dose evaluation.

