### *Tumour Response Using RECIST v1.1*

For phase I, tumour response will be evaluated using the revised RECIST guideline v1.1 (see IRC). Only subjects with measurable disease at baseline, who have received at least two

administrations of  $^{177}\text{Lu}$ -OPS201 and reached the end of Cycle 2 or EOCT visit would be considered evaluable for response.

All measurable lesions up to a maximum of two lesions per organ and five lesions in total, representative of all involved organs, should be identified as target lesions and recorded and measured at baseline.

A modified version of RECIST (“mGa-RECIST”) will also be assessed. In this second evaluation, tumours will be assessed for reading based on  $^{68}\text{Ga}$ -OPS202 and CT. There will be a tumour mapping, so that RECIST can be determined on  $^{68}\text{Ga}$ -OPS202 positive lesions. Since there is a possibility for a different set of lesions to be identified by  $^{68}\text{Ga}$ -OPS202, this provides the direct response of  $^{177}\text{Lu}$ -OPS201 on these tumours to be evaluated.

Tumour response of each subject will be graded as complete response, partial response, stable disease or progressive disease and unevaluable according to RECIST version 1.1. Based on this classification, the following endpoint will be calculated as defined by RECIST v1.1 and “mGa-RECIST”:

- ORR: proportion of subjects with a BOR characterised as either CR or PR relative to the total number of evaluable subjects.
- DCR: proportion of subjects with a BOR characterised as CR, PR or stable disease relative to the total number of evaluable subjects.
- PFS will be evaluated as defined per RECIST version 1.1.
- Tumour response using volumetric CT/MRI assessment

The same tumours identified as target lesions and assessed by “mGa-RECIST” will also be evaluated by the percentage change in volume.

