## 2.4 MTCA evaluable population

MTCA evaluable population is all subjects who received at least one dose of  $^{177}\text{Lu}$ -OPS201 in the radioactivity escalation of the phase I of the study. The MTCA-evaluable population will be used to determine the MTCA/MTSA/MACA for phase I of the study.

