#### *Peptide Mass Dose Evaluation*

In parallel with the radioactivity escalation phase, once the first cycle of a radioactivity level is considered acceptably tolerated by the DRB, the radioactivity level will be repeated with a higher peptide mass dose (700 µg ( $\pm 15\%$ )). Three additional cohorts of three to five subjects will thus be enrolled in the peptide mass dose evaluation.

The DRB for peptide mass dose escalation will meet after the third subject of each cohort has received the first cycle of  $^{177}\text{Lu}$ -OPS201 with DLT assessments performed.

The DRB will review all safety and dosimetry data and allow the peptide mass dose escalation. The cohort with the high peptide mass dose (700 µg) will thus only start when the first cycle of the corresponding radioactivity level tested with 300 µg peptide mass dose has been evaluated by the DRB and has been considered acceptably tolerated.

Moreover, the administration of the second cycle of the peptide mass dose evaluation cohorts can only proceed once the second cycle of the corresponding radioactivity level has been considered acceptably tolerated. The same subject cannot participate in the radioactivity escalation cohort and the peptide mass dose cohort.

At the time of DRB meeting, all cumulative available information will be reviewed.

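### The SAP gives two incompatible populations for Phase I tumour response, and the one named in the methods section leaves out the peptide-mass cohorts

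*SAP*

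**What the plan says.** **The population named in the methods.** Section 3.2.1.1 states: "Phase I analyses on tumour responses will be using the MTCA evaluable population". Section 2.4 defines that population as subjects with at least one dose of 177Lu-OPS201 "in the radioactivity escalation of the phase I of the study" and gives its purpose: "The MTCA-evaluable population will be used to determine the MTCA/MTSA/MACA for phase I of the study". Response is not mentioned there. Section 3.2.1.1 keeps NE and NA as best-overall-response categories, and section 3.2.14 takes percentages over all subjects in the named population.

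**The two parts of Phase I.** Section 1.2 (Treatment Period - Phase I) states: "This phase will encompass both radioactivity escalation and peptide mass dose evaluation". Section 3.2.16 (Peptide Mass Dose Evaluation) runs the second part in parallel with the first: "Three additional cohorts of three to five subjects will thus be enrolled in the peptide mass dose evaluation". The subjects are different people: "The same subject cannot participate in the radioactivity escalation cohort and the peptide mass dose cohort". Section 3.1 calls for Phase I results both by cohort and overall.

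**The second rule.** Section 1.3.2.1 (Tumour Response Using RECIST v1.1) opens its evaluability rule with "Only subjects with measurable disease at baseline, who have received at least two" administrations of 177Lu-OPS201, and adds that they must have "reached the end of Cycle 2 or EOCT visit would be considered evaluable for response". The PERCIST paragraph has a parallel rule. The Phase I endpoint definitions in section 3.1.2 divide ORR and DCR by the number of evaluable subjects and do not define the term.

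**The concern.** A programmer following sections 3.2.1.1, 2.4 and 3.2.14 would divide by every escalation subject given one dose. A programmer following sections 1.3.2.1 and 3.1.2 would divide by those who received two administrations and completed the core cycles. The same data would then give different ORR, DCR and Clopper-Pearson intervals, and the SAP has no rule of precedence.

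The two routes have different weaknesses. The first leaves out the peptide-mass cohorts, although the Phase I objective in section 1.1.2 is to describe anti-tumour activity without that restriction and Table 1 gives one imaging schedule for Phase I core treatment. No other Phase I response set exists, because the ITT and PP sets in section 2.2 cover Phase II only. The second makes membership of the denominator depend on how the subject fared.

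**Working it through.** **1. How many subjects the named population leaves out.**

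Inputs: three peptide-mass cohorts of three to five subjects (section 3.2.16) and up to 30 treated in Phase I (section 1.2.1). Assumption: three radioactivity levels, since each level is repeated at the higher peptide mass and this gives three further cohorts, with equal cohort sizes throughout.

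- At 5 per cohort: (3 + 3) × 5 = 30, which reproduces the stated maximum. Left out: 3 × 5 = 15, and 15/30 = 50%.
- At 3 per cohort: (3 + 3) × 3 = 18. Left out: 3 × 3 = 9, and 9/18 = 50%.
- The lower figure of 15 subjects in section 1.3.4 is not reproduced by six full cohorts (18). It is given there as an anticipation and not as a calculation.
- If the optional repeat cohort at the MTCA level (section 3.2.16) is also enrolled, the totals become 21 to 35, the upper one above the stated 30. The peptide-mass share is then 9/21 = 15/35 = 43%.

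**2. What the omission costs in precision.** At an assumed 20% ORR, the exact 95% interval for 3/15 is 4.3 to 48.1%, and for 6/30 it is 7.7 to 38.6%.

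**3. Which rule depends on outcome.** Section 1.3.2.10 lists radiological progression among the reasons for giving no further treatment. RECIST is read 6 weeks after each administration (Table 1). A subject who progresses at the first scan therefore has a readable result showing progression, yet cannot meet the two-administration rule and leaves the denominator. Under the one-dose rule the same subject stays in and counts as a non-responder.

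**4. Size of the denominator effect.** Rate = responders (or controlled) / denominator. The counts are illustrative assumptions: 15 escalation subjects, 3 responders, 8 with disease control, and every subject who does not complete Cycle 2 neither responding nor controlled.

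| Not completing Cycle 2 | ORR (exact 95% CI) | DCR (exact 95% CI) |
|---|---|---|
| 0 (one-dose rule) | 3/15 = 20.0% (4.3–48.1) | 8/15 = 53.3% (26.6–78.7) |
| 2 | 3/13 = 23.1% (5.0–53.8) | 8/13 = 61.5% (31.6–86.1) |
| 4 | 3/11 = 27.3% (6.0–61.0) | 8/11 = 72.7% (39.0–94.0) |
| 6 | 3/9 = 33.3% (7.5–70.1) | 8/9 = 88.9% (51.8–99.7) |

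The numerators are held fixed. A subject who responded after the first administration and then stopped would leave both numerator and denominator, so the rise is a tendency and not a certainty.

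**The case against.** The strongest reply is that the operative text is clear. Section 3.2.1.1 names one population, and the two-administration rule sits in section 1, which is headed as information taken from the protocol. On that reading early stoppers remain in the denominator, which is already most of what one would ask for in the escalation cohorts. The reply does not settle the matter, because section 3.1.2 lies inside the SAP's own methods and divides by evaluable subjects. That could mean the MTCA evaluable population or the section 1.3.2.1 set. It does establish that a reader who infers that the quoted sentence in section 3.2.1.1 itself inflates the rate would be wrong. The inflation belongs only to the two-administration rule.

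A reader might also infer that leaving out the peptide-mass cohorts biases the result. The document does not support that. Those cohorts receive 700 µg of peptide against 300 µg in the corresponding radioactivity cohorts, so they are not on an identical treatment, and a summary of the escalation cohorts alone is a legitimate quantity. What is lost is data and coverage of the treated Phase I subjects.

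Nor does the document tie Phase II to this rate. Section 1.3.4 allows the ORR thresholds to be updated from Phase I results and scientific advances. It does not require an update and gives no rule for one.

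Finally, section 5 states that the study closed prematurely and lists the outputs kept for the report. They are listings, and none shows a response endpoint. That stands and limits the practical effect.

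**Conclusion.** The point holds as an inconsistency in the written plan, of minor severity. There are two incompatible denominators for Phase I ORR, DCR and BOR and no stated precedence. The population named in the methods omits about half of the treated Phase I subjects, given three radioactivity levels and equal cohort sizes. The alternative rule removes early progressors and so tends to raise ORR and DCR. The illustrated rise in ORR, from 20.0% to between 23.1% and 33.3%, rests on assumed counts of non-completers, for which the SAP gives no figure, and it lies well inside the interval for 3/15. Phase I response is secondary and descriptive, and no test or sample size depends on it. With the report reduced to listings, the effect on what is published is now small.

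**What to change.** Define one Phase I response population: all subjects with measurable disease at baseline and at least one dose of 177Lu-OPS201, in either the radioactivity escalation or the peptide-mass cohorts. Report it by cohort, keeping the two peptide mass levels distinct, and overall, as section 3.1 already requires. Count NE and NA as non-response, and say so expressly, since section 3.2.4.1 rules out imputation and restricts analyses to observed data.

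Keep the MTCA evaluable population for DLT and MTCA/MTSA/MACA determination only. Present the two-administration subset as a sensitivity analysis. Align the RECIST and PERCIST paragraphs of section 1.3.2.1, the Phase I definitions in section 3.1.2 and the population sentence in section 3.2.1.1 with this choice.

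The cost is SAP wording. No new data are needed. The reported rate may be lower than under the two-administration rule.

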##### **Phase I**

- The summaries of BOR will include number and percentage of subjects in each of these categories (CR, PR, SD, PD, NE, NA). BOR will be assessed based on RECIST v1.1

(Eisenhauer EA, 2009). BOR by Ga-OPS202 PET mGa-RECIST, will also be analysed similarly. BOR by F-FDG-PET PERCIST v1.0 and by mGa-PERCIST will be analysed similarly as BOR by RECIST 1.1 using each of these categories (CMR, PMR, SMD, PMD, NE, NA).

- ORR over the two treatment cycles of the core study measured by the ICL. Objective response is defined as the percentage of subjects with BOR as PR and CR measured by CT or MRI using RECIST version 1.1. Tumour response assessments are performed 6 weeks after each administration of Lu-OPS201 during the core study or at the time of occurrence of first clinical signs of disease progression as determined by the investigator. The point estimates of the ORR will be calculated and accompanied by a 95% exact binomial confidence interval (CI) using the Clopper-Pearson method. ORR by Ga-OPS202 PET, mGa-RECIST will also be analysed similarly. ORR of CMR and PMR by PERCIST 1.0 and by mGa-PERCIST will be analysed similarly as ORR by RECIST 1.1.
- DCR by RECIST v1.1 defined as the percentage of subjects who have achieved a response of CR, PR or stable disease, will be analysed and summarised in the same manner as ORR.
- PFS by RECIST v1.1 will be summarised descriptively using the Kaplan-Meier method. The Kaplan-Meier estimates of the median PFS, and the corresponding 2-sided 95% confidence intervals calculated using Greenwood's formula will be presented.
- OS is defined as the time from the date of first dose of Lu-OPS201 to the date of death due to any cause. Subjects who have not died will be censored at the date of last contact which may be identified from a visit date or any study assessment (physical examination, vital signs, ECOG performance status, ECG, study drug record, radiological evaluation, laboratory sampling, concomitant or follow-up procedures), AE, medication, or disposition information. OS will be calculated using the Kaplan-Meier method. One-year and two-year survival are defined as the subject survival probability at 1 year and 2 years, respectively, after the date of first dose of Lu-OPS201. One-year and two-year survival probability along with the associated 2-sided 95% confidence intervals, will be provided. If there are a sufficient number of OS events (i.e., deaths), median OS time, first and third quartiles and associated 95% 2-sided confidence intervals, will be estimated using the Brookmeyer-Crowley method (Brookmeyer, 1982). Kaplan-Meier OS curves also will be provided.
- Change (%) in tumour volume from volumetric CT (or MRI) and sum of the diameters of the target lesion per RECIST version 1.1 from Screening to 6 weeks after each Lu-OPS201 administration (each cycle) will be summarised descriptively. Waterfall plots will be used to depict graphically for individual subjects of their best change (%) or largest reduction (%) from Screening in the sum of the diameters in target lesions. Spider and swimmer plots will be used to display the change in tumour burden over time for individual subjects and the occurrence of clinical outcomes of interest (e.g., tumour response, disease progression, treatment discontinuation, death).
- Quantitative changes (%) (SUV normalised by lean body mass (SUL)max and SULmean) in tumour-to-background 18F-FDG-PET uptake from Screening and 6 weeks after second Lu-OPS201 administration from the second cycle will be summarised descriptively. Waterfall plots will be used to depict graphically for individual subjects of their best change (%) or largest reduction (%) from Screening in SULmax and SULmean in target lesions. Spider and swimmer plots will be used to display the change in tumour burden over time for individual subjects and the occurrence of clinical outcomes of

interest (e.g., tumour response, disease progression, treatment discontinuation, death). Numbers and percentages of CMR (complete metabolic response), PMR (partial metabolic response), SMD (stable metabolic disease), and PMD (progressive metabolic disease) using PERCIST v1.0 criteria will be summarised.

- Change (%) in tumour uptake (assessed based on SUVmax and SUVmean) on Ga-OPS202 PET/CT from Screening and 6 weeks after second Lu-OPS201 administration (second cycle) will be summarised descriptively. Waterfall plots will be used to depict graphically for individual subjects of their change (%) from Screening in tumour uptake to 6 weeks after second Lu-OPS201 administration (second cycle).
- Change (%) in tumour uptake (assessed based on SUVmax and SUVmean) on Ga-OPS202-PET/CT from Screening to 6 weeks after second Lu-OPS201 administration (second cycle) will be summarised descriptively by BOR tumour response according to RECIST v1.1.
- Correlation between change (%) in tumour uptake on Ga-OPS202 (assessed based on SUVmax and SUVmean) PET/CT at baseline with tumour response to Lu-OPS201 therapy using ceCT/MRI RECIST v1.1 will be assessed. Spearman correlation coefficient and its p-value will be reported for change (%) in tumour uptake (assessed based on SUVmax and SUVmean) on Ga-OPS202-PET/CT from Screening and tumor response 6 weeks after second Lu-OPS201 administration (second cycle)
- Correlation between the number of lesion counts from Ga-OPS202 in tumour lesions expressing ssTR2 on PET/CT images at screening and the number of lesion counts from Lu-OPS201 SPECT/CT at 24 hours after the first Lu-OPS201 administration (Cycle 1) will be assessed by Pearson correlation coefficient and its p-value.

## **Phase II**

- ORR over the two treatment cycles of the core study measured by the ICL. Objective response is defined as the sum of PR and CR measured by CT or MRI using RECIST version 1.1. Tumour response assessments are performed 6 weeks after each administration of Lu-OPS201 during the core study or at the time of occurrence of first clinical signs of disease progression as determined by the investigator. The point estimates of the ORR will be calculated and accompanied by a 95% exact binomial confidence interval (CI) using the Clopper-Pearson method. ORR by Ga-OPS202 PET mGa-RECIST, will also be analysed similarly. ORR of CMR and PMR by PERCIST 1.0 and by mGa-PERCIST will be analysed similarly as ORR by RECIST 1.1.
- The summaries of BOR will include number and percentage of subjects in each of these categories (CR, PR, SD, PD, NE, NA). BOR will be assessed based on RECIST v1.1 ([Eisenhauer EA, 2009](#)). BOR by Ga-OPS202 mGa-RECIST will also be analysed similarly. BOR by F-FDG-PET PERCIST v1.0 and by mGa-PERCIST will be analysed similarly as BOR by RECIST 1.1 using each of these categories (CMR, PMR, SMD, PMD, NE, NA).
- DRR by RECIST v1.1 defined as the percentage of subjects who have achieved a response of CR, PR or stable disease, will be analysed and summarised in the same manner as ORR.
- PFS by RECIST v1.1 will be summarised descriptively using the Kaplan-Meier method. The Kaplan-Meier estimates of the median PFS, and the corresponding 2-sided 95% confidence intervals calculated using Greenwood's formula will be presented.

- OS is defined as the time from the date of first dose of  $^{177}\text{Lu}$ -OPS201 to the date of death due to any cause. Subjects who have not died will be censored at the date of last contact which may be identified from a visit date or any study assessment (physical examination, vital signs, ECOG performance status, ECG, study drug record, radiological evaluation, laboratory sampling, concomitant or follow-up procedures), AE, medication, or disposition information. OS will be calculated using the Kaplan-Meier method. One-year and two-year survival are defined as the subject survival probability at 1 year and 2 years, respectively, after the date of first dose of  $^{177}\text{Lu}$ -OPS201. One-year and two-year survival probability along with the associated 2-sided 95% confidence intervals, will be provided. If there are a sufficient number of OS events (i.e., deaths), median OS time, first and third quartiles and associated 95% 2-sided confidence intervals, will be estimated using the Brookmeyer-Crowley method ([Brookmeyer, 1982](#)). Kaplan-Meier OS curves also will be provided.
- DCR by RECIST v1.1, defined as the percentage of subjects who have achieved a response of CR, PR or stable disease, will be analysed and summarised in the same manner as ORR.
- TTP by RECIST v1.1, defined as the time from date of first dose of  $^{177}\text{Lu}$ -OPS201 to the date of first documentation disease progression as determined by the investigator, will be analysed and summarised in the same manner as PFS.
- TTR by RECIST v1.1, defined as the time from the date of first dose of  $^{177}\text{Lu}$ -OPS201 to the date of the first documentation of a response (CR or PR whichever occurs first) in a subject who responded, will be analysed and summarised in the same manner as PFS.
- DoR by RECIST v1.1, defined as the time from date of first documentation of response (CR or PR whichever occurs first) to the date of disease progression or to death due to any cause, whichever occurs first, will be analysed and summarised in the same manner as PFS.
- Change (%) in tumour volume from volumetric CT (or MRI) and sum of the diameters of the target lesion per RECIST version 1.1 from Screening to 6 weeks after each  $^{177}\text{Lu}$ -OPS201 administration (each cycle) will be summarised descriptively. Waterfall plots will be used to depict graphically for individual subjects of their best change (%) or largest reduction (%) from Screening in the sum of the diameters in target lesions. Spider and swimmer plots will be used to display the change in tumour burden over time for individual subjects and the occurrence of clinical outcomes of interest (e.g., tumour response, disease progression, treatment discontinuation, death).
- Quantitative changes (%) (SUV normalised by lean body mass (SUL)max and SULmean) in tumour-to-background  $^{18}\text{F}$ -FDG-PET uptake from Screening and 6 weeks after second  $^{177}\text{Lu}$ -OPS201 administration from the second cycle will be summarised descriptively. Waterfall plots will be used to depict graphically for individual subjects of their best change (%) or largest reduction (%) from Screening in SULmax and SULmean in target lesions. Spider and swimmer plots will be used to display the change in tumour burden over time for individual subjects and the occurrence of clinical outcomes of interest (e.g., tumour response, disease progression, treatment discontinuation, death). Numbers and percentages of CMR (complete metabolic response), PMR (partial metabolic response), SMD (stable metabolic disease), and PMD (progressive metabolic disease) using PERCIST v1.0 criteria will be summarised.
- Change (%) in tumour uptake (assessed based on SUVmax and SUVmean) on  $^{68}\text{Ga}$ -OPS202 PET/CT from Screening and 6 weeks after second  $^{177}\text{Lu}$ -OPS201

administration (second cycle) will be summarised descriptively. Waterfall plots will be used to depict graphically for individual subjects of their change (%) from Screening in tumour uptake to 6 weeks after second  $^{177}\text{Lu}$ -OPS201 administration (second cycle).

- Change (%) in tumour uptake (assessed based on SUVmax and SUVmean) on  $^{68}\text{Ga}$ -OPS202-PET/CT from Screening to 6 weeks after second  $^{177}\text{Lu}$ -OPS201 administration (second cycle) will be summarised descriptively by ORR tumour response according to RECIST v1.1.
- Correlation between change (%) in tumour uptake on  $^{68}\text{Ga}$ -OPS202 (assessed based on SUVmax and SUVmean) PET/CT at baseline with tumour response to  $^{177}\text{Lu}$ -OPS201 therapy using ceCT/MRI RECIST v1.1 will be assessed. Spearman correlation coefficient and its p-value will be reported for change (%) in tumour uptake (assessed based on SUVmax and SUVmean) on  $^{68}\text{Ga}$ -OPS202-PET/CT from Screening and tumor response 6 weeks after second  $^{177}\text{Lu}$ -OPS201 administration (second cycle)
- Correlation between the number of lesion counts from  $^{68}\text{Ga}$ -OPS202 in tumour lesions expressing sstr2 on PET/CT images at screening and the number of lesion counts from  $^{177}\text{Lu}$ -OPS201 SPECT/CT at 24 hours after the first  $^{177}\text{Lu}$ -OPS201 administration (Cycle 1) will be assessed by Pearson correlation coefficient and its p-value.
- Proportion of subjects with sstr2-positive tumour lesions by  $^{68}\text{Ga}$ -OPS202 PET/CT scans as assessed by the identification of avid lesions in subjects screened for  $^{177}\text{Lu}$ -OPS201 treatment at baseline will be summarised and analysed in the same manner as ORR.
- Changes in health-related quality of life scores from baseline to EOCT measured by EQ-5D-5L will be summarised descriptively. Frequency tables will be used to display the number and percentage of subjects of reported problems for each level and each dimension of the EQ-5D-5L by scheduled time point. Shift tables presenting the 2-way frequency tabulation from baseline to the worst post-baseline values will be presented for each dimension of the EQ-5D-5L.
- Changes in health-related quality of life scores (global health status/QoL and each functional scale) from baseline to EOCT measured by EORTC QLQ-C30 will be summarised descriptively.

